4.3. Exclusion Criteria

Subjects who meet *any* of the following exclusion criteria are not to be enrolled in this study.

- 1) Co-infection with HIV, acute hepatitis A virus (HAV) infection or chronic HBV coinfection (HBsAg positive [HBsAg+] at screening)
- 2) Decompensated liver disease defined as INR > 1.2 x ULN, platelets < 50,000/mm³, serum albumin < 3.0 g/dL, or prior history of clinical hepatic decompensation (eg, ascites, jaundice, encephalopathy, variceal hemorrhage)
- 3) Evidence of a gastrointestinal malabsorption syndrome that may interfere with absorption of orally administered medications
- 4) Chronic liver disease of non-HCV etiology (eg, hemochromatosis, Wilson's disease, alpha-1 antitrypsin deficiency)
- 5) Evidence of hepatocellular carcinoma (HCC) or other non-hematologic malignancy (with the exception of certain resolved skin cancers)

Note: liver imaging within 6 months of baseline/Day 1 is required in patients with cirrhosis to exclude HCC

- 6) History of solid organ or bone marrow transplantation
- 7) Active or recent history (\leq 1 year) of alcohol or drug abuse
- 8) Serum creatinine > 1.5 mg/dL
- 9) Estimated glomerular filtration rate < 90 mL/min/1.73m², as calculated by the Schwartz formula
- 10) Investigational agents taken within the past 28 days (except with the prior written approval of the Sponsor)
- 11) Use of any prohibited concomitant medications as described in Section 5.3
- 12) Pregnant or lactating subjects
- 13) Sexually-active males or females of childbearing potential who are not willing to use an effective method of contraception during the study (see [Appendix 4](#) for further details)
- 14) Unable to swallow the LDV/SOF FDC 90mg/400mg and the LDV/SOF FDC 22.5mg/100mg placebo tablets
- 15) Known hypersensitivity to LDV, SOF, metabolites, or formulation excipients
- 16) Subject unable to comply with the dosing instructions for study drug administration and/or unable to complete the study schedule of assessments

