6.2. Treatment Assessments (\pm 3 days)

Treatment procedures/assessments are to be completed at the end of Weeks 1, 4, 8, and 12, and ESDD as applicable, for all subjects as outlined in [Appendix 2](#).

At all visits:

- Perform symptom-directed PE and VS measurement
- Assess adverse events and concomitant medications since previous visit
- Collect blood samples for HCV RNA measurement **PPD**
- Assess study drug accountability
 - Dispense study medication at Weeks 4 and 8
- Review subject dosing diary

At Weeks 4, 8, and 12, and ESDD if applicable:

- Obtain height and body weight
- Collect blood samples for clinical chemistry and hematology
- Collect blood samples for HBV DNA only in subjects HBcAb positive at Screening
- Collect urine sample for pregnancy testing (females of childbearing potential)

At Weeks 4 and 12, and ESDD if applicable:

PPD

At Week 12 or ESDD:

- Pregnancy prevention counseling, if applicable
- Collect blood samples for Fibrotest and coagulation
- APRI Calculation

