3.7.2. Analysis Windows

Subject visits might not occur on protocol-specified days. Therefore, for the purpose of analysis, observations will be assigned to analysis windows. In general, the baseline value will be the last nonmissing value on or prior to the first dose date of study drug.

Safety laboratory data, HCV RNA, vital signs, height and weight, FibroScan, and Fibrotest, collected up to the last dose date + 3 days are considered to be on-treatment data. The analysis windows for on-treatment HCV RNA, vital signs, height and weight, and safety laboratory data are provided in [Table 3-1](#).

Table 3-1. Analysis Windows for On-treatment HCV RNA, Vital Signs, Height and Weight, Fibrotest ^a, and Safety Laboratory Data

Nominal Visit	Nominal Day	Lower Limit	Upper Limit
Baseline	1	(none)	1
Week 1	7	2	11
Week 4	28	12	42
Week 8	56	43	70
Week 12	84	71	≥85

^a Analysis windows for coagulation parameters and Fibrotest are only defined for Baseline and Week 12.

^b FibroScan is collected at screening, posttreatment week 12 and posttreatment week 24.

Safety laboratory data, HCV RNA, vital signs, height and weight, FibroScan, and Fibrotest, collected after the last dose date + 3 days will be assigned to the posttreatment follow-up (FU) visits. Visit windows will be calculated from the last dose date (ie, FU Day = collection date minus the last dose date) as shown in [Table 3-2](#).

Table 3-2. Analysis Windows for Posttreatment HCV RNA, Vital Sign, Height and Weight, FibroScan, Fibrotest, and Safety Laboratory Data

Nominal FU ^a Visit	HCV RNA, Height and Weight, FibroScan and Fibrotest			Vital Signs and Safety Laboratory Data ^b		
	Nominal FU Day	Lower Limit	Upper Limit	Nominal FU Day	Lower Limit	Upper Limit
FU-4 ^c	28	21	69	28	4	30
FU-12	84	70	146	NA	NA	NA
FU-24	168	147	210	NA	NA	NA

^a FU-x visit = posttreatment Week-x follow-up visit.

^b Vital signs and safety labs will only be summarized for the FU-4 visit (up to 30 days after last dose).

^c Doesn't apply to FibroScan and Fibrotest.

3.7.3. Selection of Data in the Event of Multiple Records in an Analysis Window

Depending on the statistical analysis method, single values may be required for each analysis window. For example, change from baseline by visit usually requires a single value, whereas a time-to-event analysis would not require 1 value per analysis window.

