7.2.1. Summaries of Numeric Laboratory Results

Descriptive statistics (n, mean, SD, median, Q1, Q3, minimum, and maximum) will be provided for ALT, aspartate aminotransferase (AST), total bilirubin, alkaline phosphatase, hemoglobin, reticulocytes, white blood cell (WBC), neutrophils, lymphocytes, platelets, activated partial thromboplastin time (APTT), International Normalized Ratio of prothrombin time (INR), creatinine and CrCL (Schwartz formula) as follows:

- Baseline values
- Values at each postbaseline time visit
- Change from baseline at each postbaseline visit

A baseline laboratory value will be defined as the final assessment performed on or prior to the date/time of first dose of study drug. Change from baseline to a postbaseline visit will be defined as the visit value minus the baseline value. The mean, median, Q1, Q3, minimum, and maximum will be displayed to the reported number of digits; SD to the reported number of digits plus 1.

Median (Q1, Q3) of the observed values for ALT, AST, total bilirubin, alkaline phosphatase, creatinine, hemoglobin, reticulocytes, WBC, neutrophils, lymphocytes, and platelets will be plotted using a line plot by visit.

In the case of multiple values in an analysis window, data will be selected for analysis as described in Section 3.8.3 (Selection of Data in the Event of Multiple Records in a Window).

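### An INR/APTT sample drawn at early discontinuation before Day 71 and within 3 days of the last dose has no analysis window, so the by-visit coagulation summary omits it.

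*SAP*

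**What the plan says.** SAP 7.2.1 lists the analytes for the numeric laboratory summary, among them "activated partial thromboplastin time (APTT), International Normalized Ratio of prothrombin time (INR), creatinine and CrCL (Schwartz formula"). For each it plans baseline values, values at each visit after baseline, and "Change from baseline at each postbaseline visit".

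SAP 3.7.2 decides which visit a value belongs to. Laboratory data "collected up to the last dose date + 3 days are considered to be on-treatment data" and go to Table 3-1. Data "collected after the last dose date + 3 days will be assigned to the posttreatment follow-up (FU) visits" and go to Table 3-2. Footnote a to Table 3-1 says: "Analysis windows for coagulation parameters and Fibrotest are only defined for Baseline and Week 12". The Week 12 row reads "Week 12 84 71 ≥85" (nominal day, lower limit, upper limit). Table 3-2 has a FU-4 window for safety laboratory data from FU Day 4 to 30 and does not exclude coagulation.

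Protocol 6.2 instructs sites, at Week 12 or ESDD: "Collect blood samples for Fibrotest and coagulation". The schedule in Protocol Appendix 2, repeated in SAP Appendix 1, marks coagulation at Screening, Day 1, Week 12 and ESDD, and at no posttreatment visit.

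**The concern.** A subject who stops early has one scheduled coagulation draw after Day 1, the ESDD draw. The coagulation windows follow the planned visits of a completer and make no provision for ESDD. The SAP also has no separate ESDD or last-value row for these tests. A prompt ESDD draw before Day 71 is on-treatment by the SAP's definition, yet it has no on-treatment window to enter.

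The omission looks unintended. Chemistry from the same visit has windows at Weeks 1, 4, 8 and 12, so the summary would show an early stopper's transaminases and bilirubin without the INR taken alongside them. SAP 7.2.2 names ESDD for APRI, so that visit was in view elsewhere in the plan.

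At stake is whether the INR and APTT tables describe everyone with a scheduled postbaseline value or mainly those who reach Day 71. Safety is one of the two primary objectives, and the study has no data monitoring committee.

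**Working it through.** No sample size, power or test enters this point. The check applies the SAP's windowing rules to every possible early stop.

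**Inputs**
- Nominal days: Week 8 = 56, Week 12 = 84 (SAP Table 3-1).
- Coagulation windows on treatment: Baseline and Week 12 only (Table 3-1, footnote a).
- On-treatment limit: last dose + 3 days (SAP 3.7.2).
- FU-4 window for safety laboratory data: FU Day 4 to 30 (Table 3-2).
- Subjects enrolled: 19 (SAP 1.3).

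**Step 1: reproduce the plan's figure.** The midpoint between Week 8 and Week 12 is (56 + 84)/2 = 70. Week 12 therefore starts on Day 71, as Table 3-1 states.

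**Step 2: place each early ESDD draw.** Let L be the days from last dose to the draw. Take last-dose days from 2 upward, with the draw on Day 70 or earlier. There are 70 − L − 2 + 1 = 69 − L such last-dose days.

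| L (days) | Last-dose days | Coagulation window |
|---|---|---|
| 0 | 69 | none, 69 of 69 |
| 1 | 68 | none, 68 of 68 |
| 2 | 67 | none, 67 of 67 |
| 3 | 66 | none, 66 of 66 |
| 4 | 65 | FU-4, 65 of 65 |
| 30 | 39 | FU-4, 39 of 39 |
| over 30 | – | none |

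Every lag from 4 to 30 days gives FU-4.

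**Step 3: compare analytes with full windows.** At L = 0 the same 69 days are all placed: Week 1 (Days 2–11) 10, Week 4 (Days 12–42) 31, Week 8 (Days 43–70) 28, and 10 + 31 + 28 = 69. ALT, AST and bilirubin from these visits are therefore summarised.

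**Step 4: what survives outside the by-visit summary.** SAP 7.2.3.1 counts a grade increase at any time after baseline up to last dose + 30 days, without visit windows. Protocol Appendix 3 grades both INR and APTT. The dropped value therefore still reaches the graded tables.

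**Step 5: size per subject.** 1/19 = 5.3%, if all 19 enrolled subjects were treated.

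**The case against.** The strongest reply is that little is lost. Footnote a matches the scheduled coagulation visits. A by-visit table shows those observed at a visit, and early stoppers are missing from the Week 12 column for every analyte. The graded tables keep the value, and SAP section 3 plans by-subject listings of collected data. What goes is one entry in a descriptive table, in a trial of 19 subjects with no hypothesis testing. All of that stands, and it limits the size of the point. It does not remove it: for the other analytes the ESDD value appears under an earlier week, while for INR and APTT it appears in no column.

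Four stronger readings are tempting, and the documents do not support them.

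- *No early ESDD coagulation value enters any numeric summary.* Footnote a belongs to Table 3-1. It cannot govern Table 3-2 as well, because it also names Fibrotest, which has FU-12 and FU-24 windows there. A draw 4 to 30 days after the last dose goes to FU-4.
- *The omitted subjects are those with suspected liver injury, so the reported INR change is biased towards none.* Protocol 7.5.1 also stops treatment for severe rash with constitutional symptoms and for related Grade 4 events. Protocol 3.6 adds pregnancy, efficacy failure, protocol violation and subject request, among others. Hepatic stops are included but do not define the group, and a direction of bias is not shown.
- *The gap affects 69/84 = 82% of treatment.* Those are days without a window, not a risk. Routine coagulation is not scheduled on them, so only an actual early stop matters.
- *The gap hides a breach of the protocol's INR limit.* The wording "Decompensated liver disease defined as INR > 1.2 x ULN" is an eligibility criterion. Nothing makes it an on-treatment limit or a planned count, and the by-visit summary would not count it for completers either.

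**Conclusion.** The point holds in a limited form. An ESDD draw before Day 71 and 0 to 3 days after the last dose is left out of the INR/APTT values and changes from baseline in SAP 7.2.1, whatever the reason for stopping. It is a stated rule that drops a collected safety value from a summary the plan promises, so it is more than missing detail.

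The effect is small: 5.3% of the Safety Analysis Set per affected subject, assuming all 19 were treated, and nil if nobody stops before Day 71. The documents do not give the number of early stoppers. SAP 2.2 describes the first 11 subjects both as completers of the treatment period and as possibly including premature discontinuations, so it sets no firm upper bound. Nor do the documents say how soon after the last dose the ESDD visit must take place, so the split between dropped draws and FU-4 draws is unknown.

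One assumption matters: that coagulation counts as safety laboratory data in Table 3-2. The protocol synopsis lists it among the safety laboratory tests. If the sponsor means otherwise, later ESDD draws before Day 71 would drop out too.

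**What to change.** In Table 3-1 footnote a and in SAP 7.2.1, add one row for INR and APTT: *last postbaseline value (Week 12 or ESDD), up to last dose + 30 days*, with change from baseline. Leave the on-treatment and FU-4 definitions unchanged. The 30-day limit matches the cut-off for laboratory summaries in SAP 7.2, and naming the row by visit rather than as on-treatment avoids a clash with the last dose + 3 days rule.

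The cost is about one sentence in the SAP and one table row, from samples already scheduled. For completers the row largely repeats Week 12, and an ESDD draw 4 to 30 days after the last dose would appear both there and under FU-4. A count of subjects with INR above 1.2 × ULN could be added, but it is optional and not part of the error. If the SAP is already final, SAP section 1 provides for documenting the change in the clinical study report.

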7.2.2. APRI Calculation

AST to Platelet Ratio Index (APRI) is assessed at screening, week 12, Early Study Drug Discontinuation (ESDD) as applicable, and Post Treatment Week 4. APRI is derived by corresponding AST, platelet value with formula: $[\text{AST (U/L)}/\text{upper limit of normal (U/L)}] \times 100/\text{platelets (}10^9/\text{L)}$. Local lab National Cancer Institute, Egypt (NCI) ULN of AST is 46 U/L. Descriptive statistics and change from baseline will be provided.

7.2.3. Graded Laboratory Values

The Gilead Grading Scale for Severity of Adverse Events and Laboratory Abnormalities will be used for assigning toxicity grades (0 to 4) to laboratory results for analysis. Grade 0 includes all values that do not meet the criteria for an abnormality of at least Grade 1. Some laboratory tests have criteria for both increased and decreased levels; analyses for each direction (ie, increased, decreased) will be presented separately.

7.2.3.1. Treatment-Emergent Laboratory Abnormalities

Treatment-emergent laboratory abnormalities are defined as values that increase at least 1 toxicity grade from baseline at any postbaseline time point, up to and including the date of last dose of study drug plus 30 days for subjects who permanently discontinued study drug, or all available data in the database snapshot for subjects who were still on treatment at the time of an interim analysis. If the relevant baseline laboratory value is missing, then any abnormality of at least Grade 1 will be considered treatment emergent.

7.2.3.2. Summaries of Laboratory Abnormalities

Laboratory data that are categorical will be summarized using the number and percentage of subjects in the study with the given response at baseline and each scheduled postbaseline visit.

The following summaries (number and percentage of subjects) for treatment-emergent laboratory abnormalities will be provided by analyte and treatment group; subjects will be categorized according to the most severe postbaseline abnormality grade for a given analyte:

- Graded laboratory abnormalities
- Grade 3 or above laboratory abnormalities

For all summaries of laboratory abnormalities, the denominator is the number of subjects with nonmissing postbaseline values up to 30 days after last dose for the laboratory parameter of interest.

A by-subject listing of treatment-emergent Grade 3 or above laboratory abnormalities will be provided by subject ID number and visit in chronological order. This listing will include all test results that were collected throughout the study for the analyte of interest, with all applicable severity grades or abnormal flags displayed.

7.3. Body Weight, Height, and Vital Signs

Vital signs (systolic and diastolic blood pressure [mmHg], pulse [beats/min]), body weight (kg), height (cm), and BMI(kg/m²) at each visit, and change from baseline at each visit will be summarized for the Safety Analysis Set using descriptive statistics (n, mean, SD, median, Q1, Q3, minimum, and maximum). The baseline value will be defined as the last available value collected on or prior to the date/time of first dose of study drug. Change from baseline to a postbaseline visit will be defined as the postbaseline value minus the baseline value.

In the case of multiple values in an analysis window, data will be selected for analysis as described in Section 3.7.3 (Selection of Data in the Event of Multiple Records in a Window). No inferential statistics will be generated.

A by-subject listing of vital signs (systolic and diastolic blood pressure [mmHg], pulse [beats/min], respiration [breaths/min], and body temperature [°C]) will be provided by

subject ID number and visit in chronological order. In the same manner, a by-subject listing of body weight, height, and BMI will be provided separately.

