Although HCV flares may occur in patients with any tumor type, they are more common in those with hematological malignancies {[Mahale 2012](#)}; leukemias and lymphomas are among the most common childhood cancers {[Ibrahim 2014](#)}. The treatment of some of these such as acute lymphoblastic leukemia (ALL) and some types of non-Hodgkins lymphoma (NHL) include induction, consolidation, and maintenance phases of chemotherapy. The maintenance phase is less intensive and may continue for 2 – 3 years.

Pediatric treatment of HCV is controversial primarily because the current treatment option (pegylated interferon [Peg-IFN] plus ribavirin [RBV]) has relatively low and variable rates of success {[Wirth 2012](#)}, (SVR24 36-53% with genotype GT1 and 55% in GT4 and > 80% in GT2 or GT3) and is limited by tolerability and severe side effects, including a potential effect on growth and development. HCV treatment is further complicated in patients receiving cancer chemotherapy.

Successful treatment of HCV infection would greatly impact liver disease outcomes and rates of liver decompensation and hepatocellular carcinoma in these pediatric patients and may facilitate treatment of their cancer.

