4.2. Inclusion Criteria

Subjects must meet all of the following inclusion criteria to be eligible for participation in this study.

- 1) Parent or legal guardian must be able to provide written informed consent prior to any screening evaluations and willing to comply with study requirements. A subject will provide assent if possible; written assent will be provided if the subject has the ability to read and write, as determined by the Ethics Committee and the Investigator's assessment.
- 2) Male or female, 12 to <18 years of age (consent of parent or legal guardian required)
- 3) Weight \geq 35 kg
- 4) Chronic HCV infection (\geq 6 months) documented by medical history or, if available, liver biopsy
- 5) HCV genotype 1 or 4 at screening
- 6) Receiving a protocol-approved maintenance chemotherapy regimen for a hematological malignancy (see Section 5.3.1)
- 7) HCV RNA \geq 1000 IU/mL at screening
- 8) Adequate hematologic function (absolute neutrophil count \geq 500/mm³, hemoglobin \geq 10 g/dL)
- 9) Treatment naïve or experienced, where treatment-experienced is defined as prior treatment failure or intolerance to a regimen including interferon with or without ribavirin that was completed at least 8 weeks prior to Baseline/Day 1
- 10) Females of childbearing potential (as defined in Appendix 4) must have a negative pregnancy test at Screening and Baseline/Day 1.
- 11) Subject able to provide written assent, if they have the ability to read and write, as determined by IRB/IEC/local requirements and Investigator's discretion

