Hemorrhage (significant acute blood loss)	NA	Symptomatic AND No transfusion indicated	Symptomatic AND Transfusion of ≤ 2 units packed RBCs (for children ≤ 10 cc/kg) indicated	Life-threatening hypotension OR Transfusion of > 2 units packed RBCs indicated (for children ≤ 10 cc/kg) indicated
Hypertension (with repeat testing at same visit)	140–159 mmHg systolic OR 90–99 mmHg diastolic	> 159–179 mmHg systolic OR > 99–109 mmHg diastolic	> 179 mmHg systolic OR > 109 mmHg diastolic	Life-threatening consequences (eg, malignant hypertension) OR Hospitalization (other than ER visit) indicated
Pediatric ≤ 17 Years (with repeat testing at same visit)	NA	91st–94th percentile adjusted for age, height, and gender (systolic and/or diastolic)	≥ 95th percentile adjusted for age, height, and gender (systolic and/or diastolic)	Life-threatening consequences (eg, malignant hypertension) OR Hospitalization indicated (other than emergency room visit)
Hypotension	NA	Symptomatic, corrected with oral fluid replacement	Symptomatic, IV fluids indicated	Shock requiring use of vasopressors or mechanical assistance to maintain blood pressure
Pericardial Effusion	Asymptomatic, small effusion requiring no intervention	Asymptomatic, moderate or larger effusion requiring no intervention	Effusion with non-life-threatening physiologic consequences OR Effusion with nonurgent intervention indicated	Life-threatening consequences (eg, tamponade) OR Urgent intervention indicated

CARDIOVASCULAR				
	Grade 1	Grade 2	Grade 3	Grade 4
Prolonged PR Interval Pediatric ≤ 16 Years	PR interval 0.21 to 0.25 sec 1st degree AV block (PR > normal for age and rate)	PR interval > 0.25 sec Type I 2nd degree AV block	Type II 2nd degree AV block OR Ventricular pause > 3.0 sec Type II 2nd degree AV block	Complete AV block Complete AV block
Prolonged QTc Pediatric ≤ 16 Years	Asymptomatic, QTc interval 0.45 to 0.47 sec OR Increase interval < 0.03 sec above baseline	Asymptomatic, QTc interval 0.48 to 0.49 sec OR Increase in interval 0.03 to 0.05 sec above baseline	Asymptomatic, QTc interval ≥ 0.50 sec OR Increase in interval ≥ 0.06 sec above baseline	Life-threatening consequences, eg, Torsade de pointes or other associated serious ventricular dysrhythmia
	Asymptomatic, QTc interval 0.450 to 0.464 sec	Asymptomatic, QTc interval 0.465 to 0.479 sec	Asymptomatic, QTc interval ≥ 0.480 sec	Life-threatening consequences, eg, Torsade de pointes or other associated serious ventricular dysrhythmia

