1.2. Study Design

This is a phase 2 single-center open-label study investigating the efficacy and safety of LDV/SOF FDC in pediatric subjects with chronic HCV who are receiving maintenance cancer chemotherapy.

Approximately 40 treatment naïve or experienced pediatric subjects will be enrolled in this study. Male and female children 12 to < 18 years of age, with genotype 1 or 4 HCV infection, and who are receiving a maintenance cancer chemotherapy regimen will be enrolled.

All subjects will receive LDV/SOF FDC once daily with or without food for 12 weeks. Subjects will be assigned to receive 1 LDV/SOF FDC 90 mg/ 400 mg tablet daily or 4 LDV/SOF FDC 22.5 mg/100 mg tablets once daily based on a swallowability assessment performed at screening up to Day 1.

Subjects who have indicated that they can take pills will be observed taking a placebo to match the 90 mg/ 400 mg LDV/SOF FDC tablet. If a subject is unable to swallow the 90 mg/ 400 mg LDV/SOF FDC tablet size, he/she will repeat the assessment with a placebo to match the 22.5 mg/ 100 mg LDV/SOF FDC tablet. If unable to swallow the 22.5 mg/ 100 mg LDV/SOF FDC tablet, the subject will be screen failed and excluded from the study.

The total time to complete all study visits is up to approximately 40 weeks including the following periods:

- 28-day (4-week) screening period
- 12-week treatment period
- Up to 24-week posttreatment period

The schedule of assessments is provided as an appendix to the SAP ([Appendix 1](#) **Error! Reference source not found.**).

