3.2. Subject Grouping

This is a single arm study. All subjects received LDV/SOF 90mg/400mg daily for 12 weeks (including 90/400mg tablet or 4 22.5/100mg tablets).

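### SAP 7.3 gives adolescent height, weight and BMI no growth reference, so its summary tables cannot tell a modest slowing of growth from normal growth (minor)

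*SAP*

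**What the plan says.** Protocol 4.2 admits adolescents ("Male or female, 12 to <18 years of age"), and SAP 3.2 states the design: "This is a single arm study". Protocol Appendix 2 has height and weight taken at screening, Day 1, Weeks 4, 8 and 12 (or early discontinuation), and post-treatment Weeks 4, 12 and 24.

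SAP 3.7.2, Table 3-2, puts these measures in the column block "HCV RNA, Height and Weight, FibroScan and Fibrotest", with windows at FU-4, FU-12 and FU-24 (the last closing on day 210 after the last dose). Vital signs and safety laboratory data get an FU-4 window only, closing on day 30.

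SAP 7.3 then describes weight in kg, height in cm and BMI in kg/m² at each visit, with change from baseline, for the whole Safety Analysis Set. The rule for change is simple subtraction: "Change from baseline to a postbaseline visit will be defined as the postbaseline value minus the baseline value". Individual values are also listed, and no inference is planned. SAP 5.2 gives the same three measures at baseline in raw units. The age and sex subsets in SAP 3.4 are for SVR12 only. The visible text contains no z-score or percentile for height, weight or BMI, no growth velocity and no growth reference.

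**The concern.** Between 12 and 18 years the expected change in height and weight is not zero, and it depends on age and sex. A raw mean change therefore combines normal growth, the age and sex mix of the sample, and any effect of illness or treatment. A control arm would supply the comparison; here there is none, and the SAP names no external reference in its place. A positive mean change could be read as reassuring while subjects were falling behind for their age.

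The protocol does raise growth. Section 1.1 lists, among the drawbacks of pegylated interferon plus ribavirin, severe side effects "including a potential effect on growth and development", and safety and tolerability is one of the two primary objectives. The SAP also follows height and weight for longer than vital signs and safety laboratory data. What is at stake is whether those extra visits yield a summary that can be interpreted.

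**Working it through.** The plan gives no figure for growth to reproduce: no expected change, SD or precision for height, weight or BMI. The arithmetic below shows only how far normal growth can move the planned summary.

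**Span of the data.** SAP 1.2 gives a "12-week treatment period" and an "Up to 24-week posttreatment period".
- To FU-24: 12 + 24 = 36 weeks, or 36/52 = 0.69 year.
- Protocol 8.6 summarises safety data to 30 days after the last dose. The last height and weight visit inside that limit is post-treatment Week 4: 12 + 4 = 16 weeks, or 16/52 = 0.31 year.

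SAP 7.6 records no departure from the protocol's safety analyses, so the documents do not settle which span applies.

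**Raw change expected with no effect.** Expected gain = height velocity × 36/52. The velocities are assumptions; the documents give none.

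| Assumed velocity (cm/year) | Gain over 36 weeks (cm) |
|---|---|
| 1 | 0.69 |
| 2 | 1.38 |
| 4 | 2.77 |
| 6 | 4.15 |
| 8 | 5.54 |

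**Mix against slowing.** Suppose a share *s* of subjects grows at 6 cm/year and the rest at 1 cm/year (assumed). The mean gain over 36 weeks is *s* × 4.15 + (1 − *s*) × 0.69.
- *s* = 50%, no slowing: 0.50 × 4.15 + 0.50 × 0.69 = 2.42 cm.
- *s* = 75%, no slowing: 0.75 × 4.15 + 0.25 × 0.69 = 3.29 cm.
- *s* = 75%, all growth slowed by 25%: 0.75 × 3.29 = 2.47 cm.

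The first and third differ by 0.05 cm. SAP 1.3 reports 19 subjects enrolled, so a move from 50% to 75% is 0.25 × 19, or about five subjects. Chance in recruitment can produce that.

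**Same comparison over 16 weeks.** The gains are 6 × 16/52 = 1.85 cm and 1 × 16/52 = 0.31 cm.
- *s* = 50%, no slowing: 0.50 × 1.85 + 0.50 × 0.31 = 1.08 cm.
- *s* = 75%, slowed by 25%: 0.75 × (0.75 × 1.85 + 0.25 × 0.31) = 1.10 cm.

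The scale is smaller and the problem is the same.

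**What a z-score changes.** With z = (observed − reference mean for that age and sex) / reference SD, a subject who tracks the reference has an expected change in z of about 0 at any age and in either sex. The summary then has a value to be compared with.

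**The case against.** Several points on the other side are sound.

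- Growth is not a visible objective or endpoint. The primary safety endpoint in protocol 8.1.4 is an adverse event that ends study drug for good. The growth remark in protocol 1.1 is about interferon plus ribavirin; the visible text names no growth concern for LDV/SOF, which is given for 12 weeks.
- The exploratory objectives, endpoints and methods are redacted in both documents. A growth analysis there cannot be excluded.
- A reader might infer that raw change hides any growth effect. The documents do not support that. Values at each visit, quartiles and extremes are reported, so a subject who lost weight would appear in the minimum, and Appendix 3 of the protocol grades unintentional weight loss from 5%. It has no matching row for slowed height or failure to gain.
- A reader might also infer that the trial cannot show whether growth was normal. That is true of the summary tables only. Individual height, weight and BMI are listed, as are demographics, and with 19 subjects each course could be set against an outside reference by hand.
- Z-scores do not supply attribution. Protocol 5.3.1 allows maintenance chemotherapy and short steroid courses, and the schedule collects no pre-treatment growth trajectory beyond screening and Day 1.
- Protocol Appendix 3 grades paediatric hypertension by percentiles "adjusted for age, height, and gender", which shows that the principle is familiar. It is no contradiction, because it comes from a general grading scale and SAP 7.3 summarises blood pressure itself in raw units.

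These points make the matter minor. They do not give the SAP 7.3 tables a reference, which is the remaining gap.

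**Conclusion.** The concern holds in a limited form. In the SAP 7.3 summary tables, a modest slowing of growth cannot be told from normal growth in a different age and sex mix, because there is neither a control arm nor a growth reference. The example gives 2.47 cm against 2.42 cm over 36 weeks, or 1.10 cm against 1.08 cm over 16 weeks. Both pairs rest on assumed velocities and an assumed two-group mix; they illustrate the problem and do not estimate anything about these subjects.

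The primary analysis and the discontinuation endpoint are unaffected. Nothing here shows that LDV/SOF affects growth, and the documents do not support reading the gap as a failure of the safety objective. It is a cheap improvement to the reporting of data already collected, conditional on the redacted exploratory section not already containing it.

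**What to change.** Unless the redacted exploratory section already does so:

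1. In SAP 5.2, add baseline z-scores for height, weight and BMI, standardised for age and sex against a named paediatric growth reference.
2. In SAP 7.3, add the same z-scores at each visit using age at that visit. (SAP 3.6 fixes age at first dose for analyses, so this needs an explicit exception.) Make descriptive change in z-score through FU-24 the main growth summary, and keep the raw values and changes as supporting.
3. State in SAP 7.3 that height and weight are summarised to FU-24, and reconcile this with the 30-day limit in protocol 8.6.
4. State that a change in z-score describes growth on study and is not attributed to LDV/SOF rather than to malignancy, chemotherapy or steroids.

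The cost is some programming; age, sex, height and weight are already collected, so no new visits or data are needed. One downside is that the reference may not match Egyptian adolescents. A constant mismatch in level would largely drop out of within-subject change, but a difference in pubertal timing need not, so the chosen reference and this limit should be reported with the results.
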